	2.4 Statistical hypotheses	
3	B Design and Outcomes	
	3.1 Descriptive endpoints	8
	3.2 Safety endpoints	10
4	4 Statistical considerations	11
	4.2 Sample size and power considerations	11
	4.3 Statistical analyzes	11
5	5 Implementation of Analysis Plan	12

1 Study synopsis

Exercise is recommended to protect physical health among people with severe mental illness and has the potential to facilitate long-term recovery ^{1–5}. An inclusive exercise community provides an opportunity for life skill training and social connectedness and may reduce the experience of loneliness and internalized stigmatization which together may improve personal recovery ^{6–8}. Using a pragmatic randomized design, we aim to examine the effectiveness of a gym-based exercise intervention tailored to young adults with severe mental illness (i.e., Vega Exercise Community) compared to usual care.

This statistical analysis plan (SAP) describes the planned analyses for the primary and secondary objectives and current planned tertiary objectives to be reported in the main article of the study. Analysis plans for subsequent articles using tertiary outcomes and additional data collected in the study will be written separately. Additional outcomes for subsequent articles are listed in the published protocol ⁹. This SAP adheres to appropriate guidelines ¹⁰ and was made publicly available before any outcome analyses commenced and before unblinding the data.

2 Study objectives

A study protocol elaborating the methods used in this study has been published ⁹.

2.1 Primary objective

The primary objective is to determine the effectiveness of participation in a supervised, gym-based exercise program in addition to usual care at four-month compared to usual care alone on patient-rated personal recovery among people with severe mental illness (primary outcome).

2.2 Secondary objectives

Secondary objectives are to examine if the gym-based exercise program in addition to usual care compared to usual care alone improves the following:

- 1. Mental health
- 2. Health-related quality of life
- 3. Behavioral and functional symptoms
- 4. Metabolic health

2.3 Tertiary objectives

As tertiary objectives to be reported in the main article, we will investigate if:

- Prolongation of subsidized gym membership in addition to motivational text messages
 (extended support) will be superior to subsidized gym membership alone (minimal support),
 and to treatment as usual in relation to post-intervention adoption of physical activity.
- 2. The exercise program is cost-effective.

2.4 Statistical hypotheses

1. Gym-based exercise training in addition to usual care will be superior to treatment as usual in relation to change in personal recovery at four months (primary outcome), mental health, health-related quality of life, behavioral and functional symptoms, and metabolic health (secondary outcomes) in young adults with severe mental illness.

3 Design and Outcomes

The trial design is outlined in Figure 1 and Table 1 outlines the outcomes. All outcomes will be obtained from all participants at baseline and all follow-ups (4months, 6months and 12months). The 12month follow-up is expected to be completed by January 2026.

Figure 1

[figure not shown]

Table 1. Primary and secondary outcomes taken at baseline, 4-month, 6-month and 12-month

Endpoint	Domain	Measure	Instrument / Method	Data supplied by	Score range and cut-off values
Primary	Recovery	Personal recovery	Questionnaire about the Process of Recovery (QPR)	Participant (rating self) and participant's primary relative (rating participant)	0-60 (higher is better) Hypothesized difference 5
Main Secondary	Mental health	Mental Component Summary (MCS)	Short-Form-12 (SF-12) Health Survey	Participant (rating self) and participant's primary relative (rating self)	0-100 (higher is better) Hypothesized difference 4
	Health- related quality of life	Physical Component Summary (PCS)		Participant (rating self) and participant's primary relative (rating self)	0-100 (higher is better)
		Physical role, bodily pain, general health, vitality, social functioning, emotional role	Short-Form-12 (SF-12) Health Survey		0-100 (higher is better)
	Behavioral and functional symptoms	Affective symptoms	The Patient-Reported Outcomes Measurement Information System (PROMIS) Emotional distress (depression)	Participant (rating self) and participant's primary relative (rating self)	Mild Moderate Severe
		Physical activity	International Physical Activity Questionnaire short form (IPAQ-SF)		No range Low, moderate, and vigorous activity and sedentary behavior
Secondary		Sleep	Pittsburgh Sleep Quality Index (B- PSQI)		Average (SD) ≤5 good sleep quality >5 poor sleep quality
		Internalized Stigma of Mental Illness	Internalized Stigma of Mental Illness Inventory (ISMI-9)	Participant (rating self)	Total score Add scores and divide by number of items answered
		Substance abuse	Self-developed items		Binary outcome (y/n): Regular/ harmful use for each substance
		Positive and negative symptoms	Modified Colorado Symptom Index (MCSI)		Total score 0-56 (higher is worse)

Endpoint	Domain	Measure	Instrument / Method	Data supplied by	Score range and cut-off values
		Loneliness	Single-item measure (4-point scale)		Binary outcome (y/n) Loneliness defined as: Cut-off ≥3
	Metabolic health	Abdominal circumference, weight	Anthropometry		Mean (SD)
		Total and visceral fat mass and muscle mass	Non-invasive bioimpedance analysis		% fat mass Kg muscle mass
		Cardiorespiratory fitness	Cycle ergometer	Blinded assessor (rating participant)	Mean (SD) mlO2/min/kg mlO2/min
		Blood pressure and resting heart rate	Digital blood pressure monitor		Mean (SD) Systolic Diastolic Rest HR Mean (SD)
		Glycosylated haemoglobin (HbA1c)	Blood samples and biochemical analysis	D (1.11.1	Mean (SD) Mmol/mol
		Blood lipids (total cholesterol, high density lipoproteins, triglycerides)			Mean (SD) Mmol/L

3.1 Descriptive endpoints

Recruitment rate will be reported using data on eligibility (y/n) and reasons for lack of interest in participating for those who are eligible. Additionally, the proportion of participants recruited through each recruitment channel (website vs. clinician referred) will be calculated. Furthermore, retention rate and reasons for withdrawal will be reported.

The following intervention-related variables will be presented descriptively:

1) Attendance to the exercise will be recorded by the instructors at every exercise class.

Attendance is reported as the total number of exercise sessions attended out of the total available sessions. Good attendance is defined as participation in 16 exercise sessions out of 48 available sessions from baseline to four months. The following will be reported:

- median (IQR), min-max, and % attendance from baseline to four months and from four months to 12 months.
- 2) Exercise intensity is collected by research staff using heart rate monitors at selected exercise classes. Average and maximum heart rate, as well as number of classes and number of participants monitored will be reported. This will be reported for all sites together.
- 3) The duration of the exercise classes will be recorded by research staff at selected exercise sessions. This will be reported as mean (SD) minutes.
- 4) Structure (i.e., warm up, resistance training, high intensity functional training (HIFT) and cooldown) will be reported by instructors at all exercise sessions using a four-point Likert scale (the higher value the better compliance with exercise protocol). Good compliance is defined as ≥3.
- 5) Organization is defined as having two instructors present at the exercise sessions. This will be collected from the work schedule of the instructors and reported as proportion of sessions with two instructors out of the total sessions during the study period. This will be reported as total for all sites.

Assessors who are blinded to group allocation perform the assessments at 4-, 6- and 12-months follow-up. Following each assessment, the assessors report whether they accidently have been unblinded (i.e., if the participant has revealed the allocation). We will calculate and report the number of blinded assessors who become unblinded.

Because anchor-based estimations of minimal clinical important difference (MCID) on the primary outcome QPR are currently not available, we will supplement the data collection with one question on perceived improvement as an external criterion ("anchor"), i.e. asking participants (on a Likert

scale of 7 levels) how they perceive their change (improvement or worsening) from last visit (1, worse than ever; 2, much worsened; 3, slightly worsened, 4, unchanged, 5, slightly improved; 6, much improved; 7, completely improved) and calculate an empirical derived anchor-based MCID

11. This anchor question is collected at all follow-up visits (4-, 6-, and 12-months).

Finally, an analysis of Number Needed to Treat (NNT) will be performed. NNT estimates the number pf people who would need to participate in the Vega Exercise Community for one person to have a MCID improvement on QPR from baseline to four months compared to the usual care group.

4.2 Sample size and power considerations

The published study protocol outlines the sample size calculations ⁹. No interim analysis will be performed. Recruitment was ended in December 2024.

4.3 Statistical analyzes

Descriptive statistical methods will be used to summarize all outcomes for both groups at each follow-up. The main analyses will evaluate the effectiveness of having access to the intervention (gym-based group exercise) applying the intention-to-treat principle with patients analyzed in the treatment group to which they were randomly allocated, adjusted for stratification variables (diagnosis and site). Secondary per-protocol analyses will target the effect of receiving the intervention. The per-protocol population will be defined as intervention group participants who attended the exercise program at least 16 of 48 times during the 4-month intervention period (baseline to four months follow-up).

The primary analysis will compare average change in QPR from baseline to four months follow-up between groups using appropriate methods for the data distribution.

For the analyses of numerical secondary and tertiary outcomes, we will use a suitable variant of (generalized) linear mixed models to account for within-subject correlations across different assessment times (baseline, 4, 6, and 12 months). Treatment arm (intervention vs usual care), time, and their interaction as well as the stratification variables site (Copenhagen, Aarhus, Aalborg) and diagnosis (F20 vs F30) will be included as fixed factors. This approach will use all available data, does not require imputation of missing data, and results are valid under the missing at random assumption. P-values and 95% CIs for relevant group differences will be presented and used to assess superiority of the intervention.

The per-protocol analyses will be adjusted with baseline covariates on diagnosis (F20, F30) and lifestyle characteristics to adjust for confounding that cannot be stratified for and that may arise when a sub-group (the per-protocol population) is analyzed ¹³. Supplementary analyses assessing the robustness of results to the definition of the per-protocol population, or analyses replacing binary group allocations with a continuous proxy of compliance (e.g. percentage of exercise sessions attended) may be included. Significance tests will be two-sided and P-values below 5% will be reported as statistically significant.

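### The primary comparison of mean QPR change names only diagnosis and site as adjustments; naming baseline QPR as a covariate would usually make it more precise at almost no cost

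*SAP*

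**What the plan says.** The primary analysis is stated in SAP section 4.3: "The primary analysis will compare average change in QPR from baseline to four months follow-up between groups using appropriate methods for the data distribution". The same section says that the main intention-to-treat analyses are "adjusted for stratification variables (diagnosis and site"). No other part of the SAP names baseline QPR as a covariate.

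The baseline value will be available. Section 3 (Design and Outcomes) says "All outcomes will be obtained from all participants at baseline and all follow-ups". Table 1 gives "Hypothesized difference 5" for QPR, without an SD.

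A longitudinal model is described, but for other endpoints: "For the analyses of numerical secondary and tertiary outcomes, we will use a suitable variant of (generalized) linear mixed models". Its fixed effects are "Treatment arm (intervention vs usual care), time, and their interaction as well as the stratification variables site", and diagnosis. The list contains no baseline covariate and no constraint that the arms share a baseline mean. Of this model the SAP says: "This approach will use all available data, does not require imputation of missing data, and results are valid under the missing at random assumption".

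Two limits apply to this reading. Section 2 notes "A study protocol elaborating the methods used in this study has been published", and section 4.2 leaves the sample size calculation to that protocol.

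**The concern.** A change score takes the whole baseline value away from the follow-up value, which fixes the baseline slope at 1. Regression on baseline estimates that slope from the data. When the true slope is not 1, the change score carries baseline noise that the regression would remove.

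The last part of section 4.3 rests the trial's conclusion on the primary outcome and gives the other outcomes a supporting role only. Section 4.2 says that recruitment has ended. Precision on this one comparison can therefore no longer come from more patients, but it can come from a covariate that is already in the data set.

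**Working it through.** **Inputs.** From the SAP: the contrast (change in QPR, baseline to four months), the named adjustments (diagnosis, site), baseline collection from all participants, and 2:1 allocation (section 5). Not in the SAP, and therefore assumed over a range: the correlation rho between baseline and four-month QPR, the two SDs, and N. The SAP states no precision or power figure that could be reproduced.

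**1. Variances.** Let k be the four-month SD divided by the baseline SD, and work in units of the baseline variance, with a common slope in both arms.
- Change score: 1 + k² − 2·rho·k
- Baseline-adjusted: k²(1 − rho²)
- Difference: (1 − rho·k)², which is zero only where rho·k = 1

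With k = 1 the ratio is (1 − rho²) / [2(1 − rho)] = (1 + rho)/2.

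**2. Equal SDs (k = 1).** The interval width scales with the square root of the ratio. The extra patients that the change score needs for equal precision are 1/ratio − 1.

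| Assumed rho | Variance ratio | Width factor | 95% CI narrower by | Extra patients |
|---|---|---|---|---|
| 0.3 | 0.65 | 0.806 | 19% | 54% |
| 0.4 | 0.70 | 0.837 | 16% | 43% |
| 0.5 | 0.75 | 0.866 | 13% | 33% |
| 0.6 | 0.80 | 0.894 | 11% | 25% |
| 0.7 | 0.85 | 0.922 | 8% | 18% |
| 0.8 | 0.90 | 0.949 | 5% | 11% |

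**3. Unequal SDs, rho 0.3 to 0.8.**
- k = 0.8: from 0.64 × 0.91 / 1.16 = 0.50 to 0.64 × 0.36 / 0.36 = 0.64.
- k = 1.25: from 1.5625 × 0.91 / 1.8125 = 0.78 to 1.5625 × 0.36 / 0.5625 = 1.00. At the upper end rho·k = 0.8 × 1.25 = 1 and the gain is nil.

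**4. Simulation.** 4,000 trials per setting, 2:1 allocation, equal SDs, site and diagnosis in both models. The empirical variance ratios at rho 0.3, 0.5 and 0.7 were 0.655, 0.746 and 0.847 with N = 90, and 0.673, 0.751 and 0.856 with N = 240. The formula gives 0.65, 0.75 and 0.85. The extra degree of freedom costs about 1.0% of variance at N = 100 and 0.5% at N = 200.

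**5. Slopes that differ by arm.** Take 200 vs 100 patients, baseline variance 1, residual variance 0.5, and slopes of 0.4 (intervention) and 1.2 (usual care).
- Pooled slope: (200 × 0.4 + 100 × 1.2)/300 = 0.667.
- Adjusted variance: (0.5 + 0.267²)/200 + (0.5 + 0.533²)/100 = 0.0107.
- Change-score variance: (0.5 + 0.6²)/200 + (0.5 + 0.2²)/100 = 0.0097.
- Ratio: 1.10, a small loss.

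With slopes of 0.5 and 0.9 the same calculation gives 0.0083/0.00885 = 0.94, again a gain.

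**6. Which models recover the precision.** One complete simulated data set, 200 vs 100, rho 0.5.
- Four-month QPR on arm, baseline, site and diagnosis, and change in QPR on the same terms, gave the same arm coefficient, 0.21750.
- The fixed effects of the secondary model, fitted to baseline and four months with known covariance, gave an arm-by-time estimate of 0.18717. This equals the raw difference in mean change. Its variance is 2(1 − 0.5) × (1/200 + 1/100) = 0.0150, which is that of the change score.

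**The case against.** The strongest reply is that this is a silence and not a wrong statement. The sentence fixes the contrast and leaves the method open. A regression of change on arm, baseline QPR, site and diagnosis would satisfy it, and the published protocol may already specify one. This stands in part. A reader might infer that the SAP rules out baseline adjustment, and the text does not support that: it names diagnosis and site but does not say that they are the only covariates. What remains is that a statistician who follows the SAP as written can stop at the less precise contrast.

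A second reply is that the planned contrast is valid and that the size of the gain is unknown. Both are true. Over the common-slope settings above, the variance ratio runs from 0.50 to 1.00.

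A third reply is that adjustment is not certain to help. This also stands. With 2:1 allocation and a single pooled slope it can lose a little, as step 5 shows, though that example needs a usual-care slope above 1.

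**Conclusion.** The point holds as an improvement in precision on the comparison that decides the trial, not as an error that invalidates it. With equal SDs and a common baseline slope, large-sample variance falls to 0.65 to 0.90 of the change-score variance for assumed rho of 0.3 to 0.8, and the 95% interval narrows by about 19% to 5%. The gain goes to nil as rho times the SD ratio (four-month over baseline) approaches 1, and it can turn into a slight loss if slopes differ strongly between arms. The algebra and the omission are certain; the size of the benefit in this trial is not.

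Three stronger readings should be resisted.
- That the trial is underpowered: the SAP gives no N, SD, correlation or power to measure a shortfall against.
- That the planned contrast is biased: under randomisation it is not. A bias through dropout would need complete-case analysis and baseline-dependent dropout in one arm only, and the SAP states neither.
- That extending the secondary mixed model to QPR would solve the matter: with complete data, its unconstrained arm effect returns the change-score contrast.

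**What to change.** In section 4.3, state that change in QPR from baseline to four months (equivalently, four-month QPR) is compared between arms as randomised by linear regression with baseline QPR, site and diagnosis as covariates, and that the adjusted mean difference is reported with its 95% confidence interval. The change wording and the hypothesis in section 2.4 can stay, because both forms give the same arm coefficient. If the protocol already names this model, repeat it in the SAP. If the primary analysis has already been run, date and disclose the change.

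The cost is one sentence, about one degree of freedom and a few lines of R, with no new data or patients. The handling of missing four-month values and how far the method should be fixed in advance are separate questions, which the precision argument does not settle.

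### In the SAP 4.3 mixed model, site and diagnosis have virtually no effect on a change-from-baseline contrast, and the SAP does not say which contrast it will report

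*SAP*

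**What the plan says.** SAP 4.3 first says that the main intention-to-treat analyses are adjusted for diagnosis and site. For numerical secondary and tertiary outcomes it then calls for a suitable (generalized) linear mixed model in which baseline is one of the four modelled assessment times. The fixed part is listed: "Treatment arm (intervention vs usual care), time, and their interaction", and "the stratification variables site (Copenhagen, Aarhus, Aalborg) and diagnosis (F20 vs F30) will be included as fixed factors". Arm-by-time is the only interaction named, and nothing constrains the two arms to a common baseline mean.

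The contrast is not fixed. The section says only that "P-values and 95% CIs for relevant group differences will be presented and used to assess superiority of the intervention". The hypothesis in SAP 2.4 is that the intervention "will be superior to treatment as usual in relation to change in personal recovery at four months (primary outcome), mental health, health-related quality of life" and the further secondary domains. There the word change is attached to personal recovery, and the secondary outcomes follow in the same list. On missing data, SAP 4.3 says: "This approach will use all available data, does not require imputation of missing data, and results are valid under the missing at random assumption".

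**The concern.** A site or diagnosis term without a time interaction shifts a participant's expected outcome by the same amount at every visit. Change from baseline subtracts that shift away. Someone who codes the listed terms and reads off the arm-by-time coefficient would therefore report an analysis labelled as adjusted for the stratification variables that is, in effect, unadjusted.

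Change is a natural reading: baseline is modelled as an outcome, arm-by-time is in the model, and the primary analysis compares change. It is not the only reading. A difference between arms at one visit also fits the wording, and it behaves differently.

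The choice matters for MCS, the main secondary outcome in Table 1, because these P-values are to be used to assess superiority. SAP section 5 says the statistician cannot be blinded, so a contrast left open now would be chosen with knowledge of allocation.

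**Working it through.** The SAP gives no figure on this point, so there is none to reproduce.

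**Inputs from the SAP.** Four visits including baseline; fixed terms as listed in 4.3; three sites and two diagnosis groups; 2:1 allocation (section 5); two-sided 5% tests (4.3); hypothesized MCS difference of 4 (Table 1).

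**Assumed inputs.** Sample size (the SAP refers to the published protocol), SD 10, correlation 0.5 between visits, size of the stratum effects, and amount of missing data.

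**Step 1, algebra.** Write the linear model as Y_it = μ_t + β_t·A_i + γ'S_i + e_it, with A the arm and S the site and diagnosis indicators. With complete data and a common covariance matrix, generalized least squares gives β̂_t = D_t − γ̂'D_S. Here D_t is the difference in arm means at visit t, and D_S is the difference in the arm means of S. The second term is the same at every visit, so β̂_4m − β̂_0 = D_4m − D_0. That is the unadjusted difference in mean change, whatever the sample size, SD or correlation.

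**Step 2, numerical check.** One simulated complete data set, N = 400, unstructured covariance, strata affecting both level and change:

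| Model | Change contrast at 4 months (SE) | Arm difference at 4 months (SE) |
|---|---|---|
| No strata | 4.223 (1.118) | 3.925 (1.234) |
| Strata as main effects, as listed in 4.3 | 4.223 (1.118) | 4.638 (1.017) |
| Strata by time | 4.651 (1.095) | 4.738 (1.019) |
| Common baseline, strata as main effects | 4.468 (0.914) | same contrast |
| Common baseline, strata by time | 4.700 (0.908) | same contrast |

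The first two rows agree exactly for change. For the difference at a visit, the main effects do act.

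**Step 3, missing data.** The cancellation becomes approximate. With unstructured covariance, adding strata main effects moves the change estimate from 4.117 to 3.815 (N = 200, 35% missing) and from 4.483 to 4.425 (N = 400, 20% missing). The SE moves by less than 1% in both cases (1.848 to 1.836; 1.228 to 1.221).

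**Step 4, cost of leaving strata out of the change contrast.** If strata explain a fraction R² of the variance in change and randomisation is balanced within strata, the reported SE is too large by the factor 1/√(1 − R²), and the actual type I error is 2·[1 − Φ(1.96/√(1 − R²))].

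- R² = 6.5%: 1/√0.935 = 1.034; 1.96 × 1.034 = 2.027; type I error about 4.3%.
- R² = 12.8%: 1/√0.872 = 1.071; 1.96 × 1.071 = 2.099; type I error about 3.6%.

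**Step 5, gain from a common baseline mean.** With equal SDs and correlation ρ between baseline and 4 months, and ignoring strata, the SE of the change contrast is SD·√[2(1 − ρ)]·√(1/n₁ + 1/n₂). With a common baseline mean it is close to SD·√(1 − ρ²)·√(1/n₁ + 1/n₂). For an assumed 240 and 120 participants, SD 10 and ρ = 0.5:

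- change: 10 × 1 × √0.0125 = 1.118;
- common baseline: 10 × 0.866 × √0.0125 = 0.968.

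This is a reduction of about 13%. In the table, strata by time alone lowers the SE by about 2% (1.118 to 1.095), while the common baseline with strata by time lowers it by about 19% (1.118 to 0.908).

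**The case against.** The strongest reply is that the SAP never commits to a change contrast. For a difference at a visit, the listed terms do adjust (SE 1.234 to 1.017 above). This stands, so a reader who infers that the promised adjustment is absent from every secondary result goes too far. But that contrast keeps any chance difference between arms at baseline, because the arm effect there is free. Neither reading makes full use of the design.

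Second, the SAP allows a suitable variant and generalized models, and the cancellation does not carry over to non-identity links. In a simulated binary outcome with a logit link, the arm-by-time coefficient moved from −0.653 to −0.730 when strata were added. This also stands, although the paragraph concerns numerical outcomes, for which a linear model is the usual choice. The freedom to choose a variant does not replace the fixed terms that the next sentence lists.

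Third, a reader might infer bias, or that the missing-at-random statement fails. Bias could arise if retention differed by arm and site and sites also differed in change. Nothing in the SAP indicates such a pattern. An assumed steep pattern (site changes of 8, 5 and 2 points; usual-care retention 90%; intervention retention 95%, 80% and 65% by site) gave 0.25 points, and a milder one 0.06, against a hypothesized MCS difference of 4. With complete data, randomisation keeps the change contrast unbiased.

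Fourth, the secondary analyses are declared exploratory and the trial's conclusion rests on the primary outcome, which this model does not analyse. That limits the stakes, and the tests err on the conservative side.

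**Conclusion.** The concern holds in limited form. If the secondary effect is change from baseline in a linear model, site and diagnosis as time-constant terms leave it virtually unadjusted, contrary to the general statement in SAP 4.3. The complete-data identity needs no assumption about sample size, SD or correlation. Near-cancellation with missing data was seen in simulation only.

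The consequence is lost precision and slightly conservative tests: SEs 3% to 7% too large and type I error of about 4.3% to 3.6%, if strata explain 6.5% to 12.8% of the variance in change. The SAP gives no basis for that share, so the range is illustrative. There is no excess of false positives from this source and no threat to the primary conclusion. The point is worth acting on because the plan leaves the contrast open and the remedy is nearly free.

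**What to change.** In SAP 4.3, state that the contrast for numerical secondary outcomes is the arm difference at each follow-up visit, with 4 months as the visit for MCS. Take it from a model with one pre-randomisation mean for both arms (no arm effect at baseline), arm by follow-up time, site by time and diagnosis by time. With a common baseline mean, the difference at a visit and the difference in change are the same quantity, so the ambiguity disappears.

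The cost is one sentence and one model line. The stratum-by-time terms add 3 stratum contrasts × 3 follow-up visits = 9 fixed-effect degrees of freedom, and dropping the baseline arm effect returns 1, a net 8. No new data are needed. If not every stratum-by-time term can be estimated, the common baseline mean should be kept, since most of the gain comes from it.
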